2.4.5.4 Analyses of vital sign variables

The summary statistics (including number, mean, median, standard deviation, minimum and maximum) of all vital signs variables (values and changes from baseline) will be calculated for each visit (baseline and post-baseline time points) by treatment group. For parameters heart rate, systolic and diastolic blood pressures, the last on-treatment and worst on-treatment value will also be provided.

The incidence of PCSAs at any time during the TEAE period will be summarized by treatment arm irrespective of the baseline level and according to the following baseline status categories (only for SBP and DBP):

- Normal/missing.
- Abnormal according to PCSA criterion or criteria.

Listing will be provided with flags indicating the out of range values as well as PCSA values.

2.4.5.5 Analyses of electrocardiogram variables

The summary statistics (including number, mean, median, standard deviation, minimum and maximum) of all ECG variables (values and changes from baseline) will be calculated for each visit (baseline and post-baseline time points) by treatment group.

The incidence of PCSAs at any time during the TEAE period will be summarized by treatment group irrespective of the baseline level and according to the following baseline status categories:

- Normal/missing.
- Abnormal according to PCSA criterion or criteria.

Listing will be provided with flags indicating the out of range values as well as PCSA values.

2.4.6 Analyses of pharmacokinetic variables

C_{trough} concentrations of SAR156597 in plasma will be described on the PK population for each time point by treatment group using descriptive statistics (number of patients, arithmetic mean (SD), geometric mean, coefficient of variation, minimum and maximum).

In a separate table, $C_{trough,av,ss}$ and $C_{Follow-up}$ will be described on the PK population by treatment group using descriptive statistics (number of patients, arithmetic mean (SD), geometric mean, coefficient of variation, minimum and maximum).

The graphical representation of time profiles for C_{trough} concentration (mean \pm SD or Median, as appropriate) will be also provided by treatment group. Average steady state achievement will be performed by visual inspection of mean plots.

According to study results, additional plots will be prepared, as deemed necessary (eg, to explore the relationship with some safety or efficacy endpoints of interest).

The results of population PK modeling will be reported separately from the study report.

2.4.7 Analyses of immunogenicity data

The following summaries will be performed on the ADA population, taking into account all samples regardless of timing in relation to injections:

- ADA results (negative, positive or inconclusive) by time point and by treatment arm.
- Neutralizing status (inconclusive or positive) for positive ADA by time point and by treatment arm.

- ADA titers using descriptive statistics (median, Q1, Q3, minimum and maximum) for positive ADA by time point and by treatment arm.
- Number (%) of patients with pre-existing ADA and number (%) of patients with treatment-emergent ADA positive response by treatment arm.
- Number (%) of patients with persistent/transient/indeterminate treatment-emergent ADA positive response by treatment arm.
- Time to onset of treatment-emergent ADA positive response (in days) using descriptive statistics by treatment arm and also according to peak titer.
- Duration of ADA (in days, only for subjects with at least 2 positive ADA samples) using descriptive statistics by treatment arm.

Correlations between ADA parameters (eg, titers, treatment-emergent ADA positive status, neutralizing status) and PK, safety and/or main efficacy endpoint(s) will be explored (eg, scatter plot) according to the study results.

2.4.8 Analyses of Biomarker data

The biomarkers will be summarized by treatment arm and time-point: number of values below Lower Limit of Quantification (LLOQ), mean, SD. The biomarkers may be log-transformed based on their distribution. A biomarker could be discarded from the analysis if too many values are missing or below LLOQ. In addition, the values below LLOQ will be imputed by LLOQ/2.

To assess the effect of SAR156597 on each biomarker, the change from baseline to Week 24 will be analyzed using a mixed model for repeated measures with treatment, visit and treatment-by-visit interaction as fixed effects, baseline biomarker value as fixed covariates, and assuming an unstructured covariance structure.

The biomarkers at baseline will be tested one-by-one for a potential prognostic and predictive effect for mRSS endpoint. The change from baseline of mRSS to Week 24 will be assessed using biomarker main effect (prognostic effect), treatment effect, randomization stratum (as per IRT) and interaction between biomarker and treatment (predictive effect). As a second step, the biomarkers will be dichotomized using median value.

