1 OVERVIEW AND INVESTIGATIONAL PLAN

1.1 STUDY DESIGN AND RANDOMIZATION

This study will be a multinational, randomized, double blind, placebo controlled, 2 parallel groups, proof of concept Phase 2 study to assess the efficacy and safety of SAR156597 200 mg administered subcutaneously once a week over a 24 week period to patients with diffuse Systemic Sclerosis (SSc).

After a screening phase of up to 4 weeks, patients will be centrally randomized (using allocation from block randomization schedule with stratifying factors) via Interactive Response Technology (IRT) in a 1:1 ratio to 1 of the 2 treatment groups and treated double-blind for approximately 6 months.

Randomization will be stratified based upon the patients' medical history of SSc ILD (yes or no).

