2.4.4.1 Analysis of primary efficacy endpoint(s)

2.4.4.1.1 Primary efficacy analysis

The primary estimand will be the difference in mean change from baseline to 24 weeks in mRSS in all randomized patients, regardless of whether or not patients completed the treatment period. This estimand corresponds to a “treatment policy strategy”.

A spaghetti plot presentation of individual data by treatment group will be presented.

The change in mRSS from baseline to Week 24 will be analyzed in the ITT population using a MMRM approach. All post-baseline data available from Week 4 to Week 24 analysis windows will be included in the analysis, regardless of adherence to treatment. The lower the mRSS is, the better it is for the patient.

Missing data will be accounted for by the MMRM. The model includes the fixed categorical effects of treatment group (placebo, SAR156597), randomization strata (as per IRT, SSc-ILD: Yes/No), time point (Week 4, Week 8, Week 12, Week 24 as defined in [Section 2.5.4](#)), randomization strata-by-time point interaction and treatment-by-time point interaction, as well as the continuous fixed covariates of baseline mRSS value and baseline value-by-time point interaction.

This model will be run using SAS Mixed procedure. The repeated-measures analysis will be based on the restricted maximum likelihood method (Newton-Raphson algorithm) assuming an unstructured correlation matrix to model the within-patient errors. Denominator degrees of freedom will be estimated using Kenward-Roger approximation. This model will provide baseline adjusted LSmeans estimates at Week 24 for both treatment groups with their corresponding standard errors (SEs) and 95% confidence intervals (CIs). To compare SAR156597 to the placebo group, an appropriate contrast statement will be used to test the difference of these estimates at the 5% one-sided alpha level. The 95% and 90% confidence intervals of the difference will be provided. Let μ_0 and μ_1 be the population means of the change from baseline in mRSS at Week 24 under placebo and SAR156597, respectively. The null hypothesis that will be tested is “ $H_0: \mu_0 = \mu_1$ ” versus “ $H_1: \mu_0 > \mu_1$ ”.

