2.4.4.2 Analyses of secondary efficacy endpoints

All secondary endpoints are described in [Section 2.1.3.2](#) and will be analyzed using the ITT population.

Change in continuous secondary efficacy endpoints (HAQ-DI composite score, observed FVC, observed DLco [corrected for hemoglobin]) from baseline to Week 24 will be analyzed using the same MMRM model as for the primary endpoint. Specifically, the model will contain fixed categorical effects of treatment group (placebo, SAR156597), randomization strata (as per IRT, SSc-ILD: Yes/No), time point (Week 4 [only for HAQ-DI], Week 8 [only for HAQ-DI], Week 12 and Week 24), randomization strata-by-time point interaction and treatment-by-time point interaction, as well as the continuous fixed covariates of corresponding baseline value and baseline-by-time point interaction. All post-baseline data available from Week 4 for HAQ-DI, Week 12 for FVC and DLco, to Week 24 analysis windows will be included in the analysis, regardless of adherence to treatment. Missing data will be accounted for by the MMRM. The studentized residuals of the MMRM will be analyzed as for the primary endpoint.

This model will provide baseline adjusted LSmeans estimates at Week 24 for both treatment groups with their corresponding standard errors (SEs) and 95% CIs. The SAR156597 to placebo difference of these estimates will be provided with its corresponding 95% and 90% CIs and p-value.

Within each randomization stratum (as per IRT, SSc-ILD: Yes/No), baseline adjusted LSmeans estimates at Week 24 will also be provided for both treatment groups with their corresponding SEs and 95% CIs, as well as their difference with the corresponding 95% and 90% CIs.

In order to assess the robustness of the analyses to randomization stratum mistakes (ie, the stratum recorded in IRT differs from the actual one), if more than 15% of patients have been randomized to the wrong stratum, the MMRM model will be re-run including the actual stratum as per the eCRF instead of the stratum recorded in IRT.

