2.4.4.4 Analyses of exploratory efficacy endpoints

All exploratory endpoints are described in [Section 2.1.4](#) and will be analyzed using the ITT population unless otherwise specified.

Change in continuous exploratory efficacy endpoints from baseline to Week 24 will be analyzed using the same MMRM model as for the primary and continuous secondary efficacy endpoints. Specifically, the model will contain fixed categorical effects of treatment group, randomization strata (as per IRT), time point, randomization strata-by-time point interaction and treatment-by-time point interaction, as well as the continuous fixed covariates of corresponding baseline value and baseline-by-time point interaction. All post-baseline data available from Week 4 to Week 24 analysis windows will be included in the analysis, regardless of adherence to treatment. Missing data will be accounted for by the MMRM. This model will provide baseline adjusted LSmeans estimated at Week 24 in both treatment groups with their corresponding 95% CIs. The SAR156597 to placebo differences of these estimates will be provided with its corresponding 95% and 90% CIs and p-value.

Change in continuous exploratory efficacy endpoints from baseline to Week 35 will be analyzed using the same model. All post-baseline data available from Week 4 to Week 35 analysis windows will be included in the analysis, regardless of adherence to treatment.

2.4.4.4.1 mRSS

Responder rates (proportion of patients with an improvement from baseline in mRSS of at least 20%, 40% and 60%) at Week 24 and Week 35 will be analyzed using a logistic regression with the categorical effects of treatment group and randomization strata (as per IRT) and the continuous effect of mRSS at baseline. This model will provide the SAR156597 to placebo odds ratio estimate and its 95% and 90% confidence intervals. The p-value will be obtained from the

Wald Chi-square test. Patients with missing value at Week 24, respectively Week 35, will be considered as non-responders. Cumulative distribution function (CDF) graphs will be also presented (percentage of patients according to the relative improvement from baseline in mRSS) at W24 and W35.

Furthermore, the change from baseline to Week 35 will be analyzed using the MMRM model described in [Section 2.4.4.4](#).

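### The model for the drug's effect on each biomarker (SAP 2.4.8) omits the SSc-ILD randomization stratum without explanation; if the stratum is prognostic, the reported standard errors are conservative

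*SAP*

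**What the plan says.** SAP 1.1 (Study design and randomization) allocates patients "in a 1:1 ratio to 1 of the 2 treatment groups", stratified by medical history of SSc-ILD (yes or no).

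SAP 2.4.8 (Analyses of Biomarker data) contains two models.

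- **Effect of the drug on each biomarker.** Change from baseline to Week 24 is analyzed with a "mixed model for repeated measures with treatment, visit and treatment-by-visit interaction as fixed effects, baseline biomarker value as fixed covariates", with an unstructured covariance. The list has no stratum, stratum-by-visit or baseline-by-visit term.
- **Prognostic and predictive value of baseline biomarkers for mRSS.** This model contains the biomarker main effect, "treatment effect, randomization stratum (as per IRT) and interaction between biomarker and treatment (predictive effect").

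The efficacy MMRMs all carry the stratum:

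- **Primary (SAP 2.4.4.1.1):** stratum as per IRT, plus "randomization strata-by-time point interaction and treatment-by-time point interaction, as well as the continuous fixed covariates of baseline mRSS value". The model also lets the baseline slope differ by time point.
- **Secondary (SAP 2.4.4.2):** the same structure for HAQ-DI, observed FVC and observed DLco.
- **Exploratory (SAP 2.4.4.4):** the same structure again, with the IRT stratum and its interaction with time.

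Protocol 11.4.7 calls the biomarker analysis exploratory and leaves the details to the SAP.

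**The concern.** Stratified randomization balances SSc-ILD history between the arms by design, and the analysis gets the benefit only if the model accounts for the stratum. If the stratum is related to the outcome and is left out, the between-stratum variation stays in the residual. The model then reports a standard error larger than the true sampling error of the estimate.

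Measuring the effect on disease and IL-4/IL-13 pathway biomarkers is a listed exploratory objective (Protocol 5.3, SAP 1.2.3). SAP 2.4.8 is where that analysis is specified, and among the treatment-effect MMRMs named above it is the only one without the stratum. At stake is some precision in the pharmacodynamic comparison, plus an unexplained inconsistency that is easily removed before the data are analyzed.

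**Working it through.** **1. The plan's own figure.** The only design figure is the power for mRSS (SAP 1.3): 47 per arm, difference 3.6, SD 7, one-sided alpha 5%.

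- 3.6 / (7 × √(2/47)) = 2.493
- 2.493 − 1.645 = 0.848, and Φ(0.848) = 80.2%

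The stated 80% reproduces (79.7% with the noncentral t). It concerns mRSS and does not depend on the biomarker model. The documents give no power, variance or effect size for any biomarker.

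**2. Terms side by side.**

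| Model | Stratum | Stratum × time | Baseline | Baseline × time |
|---|---|---|---|---|
| Primary MMRM, 2.4.4.1.1 | yes | yes | yes | yes |
| Secondary MMRM, 2.4.4.2 | yes | yes | yes | yes |
| Exploratory MMRM, 2.4.4.4 | yes | yes | yes | yes |
| Biomarker effect MMRM, 2.4.8 | no | no | yes | no |

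The sentence in 2.4.8 is complete, and no general rule elsewhere in the SAP supplies the missing terms.

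**3. Size of the effect on the standard error.** Let R² be the share of the residual variance, after treatment and baseline, that the stratum explains. With 1:1 allocation within strata, the treatment estimate and its true sampling error hardly change when the stratum is dropped, but the residual variance is inflated by 1/(1 − R²). So:

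- SE ratio (omitted / included) ≈ 1/√(1 − R²)
- Null rejection of a nominal two-sided 10% test ≈ 2 × [1 − Φ(1.645/√(1 − R²))]

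R² is an assumption, because the documents do not give it. The 10% level is only a yardstick, matching the 90% confidence intervals used for the efficacy endpoints.

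| Assumed R² | 1/√(1 − R²) | Excess SE | 1.645 × ratio | Null rejection at nominal 10% |
|---|---|---|---|---|
| 0 | 1.000 | 0% | 1.645 | 10.0% |
| 0.05 | 1.026 | 2.6% | 1.688 | 9.15% |
| 0.10 | 1.054 | 5.4% | 1.734 | 8.3% |
| 0.20 | 1.118 | 11.8% | 1.839 | 6.6% |

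**4. Check by simulation.** N = 94, 1:1 within strata, ANCOVA at a single visit as a simplification of the MMRM, 10,000 runs per setting, with an assumed 50% or 70% of patients in the SSc-ILD stratum.

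- The 95% interval width ratios for R² = 0, 0.05, 0.10 and 0.20 were 1.000, 1.026, 1.055 and 1.120.
- Coverage with the stratum omitted rose from about 95% at R² = 0 to about 96% at 0.05 and 0.10 and about 97% at 0.20. With the stratum included it stayed near 95%.
- The ratio of true sampling standard errors was 1.000 to 1.002, so the estimate itself is barely affected.

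A further simulation with assumed strata of 56 and 38 gave null rejection rates of 10.0%, 9.2%, 8.2% and 6.6%, in line with the formula.

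**The case against.** The strongest defense is that the consequence is conditional and small. SAP 2.4.8 specifies no confidence interval, significance level or decision rule for this model. Biomarkers are described separately from the efficacy endpoints (Protocol 9.3.3, SAP 2.1.8) and are analyzed in their own population of treated patients with samples (SAP 2.3.5), not in the ITT population. The second model in 2.4.8 has mRSS as its outcome, so the stratum there does not prove that its absence for a biomarker outcome was a slip. A common baseline slope across visits is a defensible, parsimonious choice. Adjustment for the baseline biomarker may already absorb much of any association with SSc-ILD.

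Most of this stands, and it limits the point to a minor one. It does not supply a reason for leaving out a factor by which the trial randomizes.

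A reader might infer that the biomarker intervals *are* too wide. The documents do not support that: it requires SSc-ILD history to predict biomarker change after baseline adjustment, and they give no figure for any of the five named markers. A reader might also infer that the biomarker comparison is biased or that its type I error is inflated. Neither follows, because any error is in the conservative direction.

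**Conclusion.** The omission is a matter of text and is clear. Its consequence depends on an unknown. For an R² between 0 and 0.10, the standard error is overstated by 0% to about 5.5%. At 0.20, which would be a strong association, it is overstated by about 12%. These figures rest on the assumed R², on 1:1 balance within strata, on N = 94 (the biomarker population may be smaller) and on a single-visit approximation to the MMRM.

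The discrepancy should not be read as a departure within the efficacy analyses. The biomarker analysis is exploratory, and the documents give it no role in the primary or secondary conclusions. Severity is minor.

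**What to change.** In SAP 2.4.8, add randomization stratum (as per IRT) and stratum-by-visit to the MMRM for the effect of SAR156597 on each biomarker. Optionally add baseline-by-visit, so that the model matches Section 2.4.4.4. If the omission was deliberate, state why.

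The cost is one sentence of SAP text and about one degree of freedom per added term. No new data are needed, since the stratum is already recorded in the IRT. If the stratum turns out to explain nothing, the loss of precision is negligible: the simulated interval width ratio at R² = 0 was 1.000 after rounding.

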1.2.3 Exploratory objectives

The exploratory objectives are:

- To explore the efficacy of SAR156597 compared to placebo on other manifestations of SSc (gastrointestinal, joint pain, cardiovascular and renal manifestations) in patients with dcSSc.
- To explore the effect of SAR156597 on the Quality Of Life in patients with dcSSc.
- To measure the effect of SAR156597 on biomarkers of the disease activity and the IL 4/IL 13 pathway.
- To identify biomarkers predictive of response to treatment as defined by mRSS endpoints.

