The 100 complete datasets will be then analyzed using an ANCOVA model with treatment group and randomization strata (as per IRT, as defined in [Section 1.1](#)) as fixed effects, and the baseline mRSS value as continuous covariate, and change in mRSS from baseline to Week 24 as explained variable. The MIANALYZE SAS procedure will be used to generate valid statistical inferences by combining results from the 100 analyses using Rubin's formulae.

The number of imputations (100) will be informally verified by replicating sets of 100 imputations and checking whether the combined results are stable. If not stable, the number of imputations will be increased and informally checked as above, and thus until stable estimates are obtained.

Non continuous variables included in the imputer's model (ie, treatment group, randomization strata) are not expected to be missing.

Only imputed values during the on-treatment period will be kept in the final datasets that will be analyzed using ANCOVA. Imputed values during the post-treatment period will be discarded and replaced by imputed values described in the next paragraph.

Imputation programming

In order to implement the control-based pattern imputation, we will break the imputation process into a sequence of multiple calls to PROC MI, where each call is intended to impute missing values at one time-point only. The general logic of such a strategy is as follows.

1. With each call to PROC MI, impute only one time-point using a regression-based MI method for monotone missingness. Variables included in the regression model are randomization strata and mRSS values from previous time-points (including baseline).
2. When imputing missing values for time-point t , the input dataset should include all control patients, but only those patients from the experimental arm who have values at time-point t missing (only those who need imputation at time-point t). Since patients from the experimental arm with non-missing values at time-point t are not included in the input dataset, they will not contribute to the estimation of an imputation model for time-point t . The imputation model will then be estimated using control patients only, while this call to PROC MI will impute missing data at time-point t for all patients who need imputation at that time-point. This way, patients from experimental arm will be imputed based on the control patients' model. Note that treatment arm should not be included as an effect in this model.

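### The SAP 2.4.8 model relating baseline biomarkers to mRSS change leaves out baseline mRSS, so the predictive interaction is estimated less precisely than it could be and the prognostic term cannot show value beyond baseline skin severity

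*SAP*

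**What the plan says.** SAP 1.2.3 lists as an exploratory objective: "To identify biomarkers predictive of response to treatment as defined by mRSS endpoints". SAP 2.4.8 serves it. "The biomarkers at baseline will be tested one-by-one for a potential prognostic and predictive effect for mRSS endpoint". The model has four terms: the outcome "will be assessed using biomarker main effect (prognostic effect), treatment effect, randomization stratum (as per IRT) and interaction between biomarker and treatment (predictive effect". Then: "As a second step, the biomarkers will be dichotomized using median value". The section does not mention baseline mRSS, does not refer back to the primary model and gives no rule for calling a biomarker prognostic or predictive. Protocol 11.4.7 leaves the details to the SAP, so nothing else supplies the missing term.

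The SAP's other mRSS models include it:

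- The primary MMRM (2.4.4.1.1) has "the continuous fixed covariates of baseline mRSS value and baseline value-by-time point interaction". The on-treatment, rater, high-mRSS and subgroup analyses re-run or extend that model.
- The ANCOVA after control-based imputation (2.4.4.1.7) has "the baseline mRSS value as continuous covariate".
- The responder logistic regressions (2.4.4.4.1) include mRSS at baseline.

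Within 2.4.8, the model for change in a biomarker adjusts for that biomarker's own baseline value.

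**The concern.** Change from baseline usually depends on where the patient started. Eligible baseline scores run from 10 to 35 (Protocol 7.2, E 03) and the scale stops at 0, so a patient entering at 10 can improve by at most 10 points and one entering at 35 by up to 35. If baseline mRSS explains part of the change, leaving it out puts that part into the residual and widens the interval for the interaction. With about 94 patients and one-by-one testing, precision for an interaction is scarce.

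The main effect raises a second question. Randomization balances the treatment arms, not biomarker levels. A biomarker that follows skin severity may relate to mRSS change only because baseline mRSS does. The four-term model cannot separate that from prognostic information a clinician does not already have from the skin score.

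**Working it through.** **Inputs from the documents.** 94 patients, 47 per arm; SD of change 7; difference 3.6; one-sided alpha 5% (SAP 1.3). Model terms as in SAP 2.4.8.

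**Inputs assumed.** The documents give no correlation between baseline mRSS and its change (size r, negative sign) or between a biomarker and baseline mRSS (q). I take 0.3 to 0.5 for each and also show weaker r. All 94 patients are taken to have data, and baseline mRSS is taken not to modify the treatment effect.

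**Check of the plan's own figure.** 3.6 / (7 × √(2/47)) = 3.6 / 1.444 = 2.493; 2.493 − 1.645 = 0.848; Φ(0.848) = 80.2%. The stated 80% reproduces, so these inputs are a sound basis. SAP 2.4.8 gives no figure of its own.

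**Two mechanisms.** Neither document says why baseline and change would be correlated, so I use two extremes.

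- A: change depends on the observed baseline score, and the biomarker relates to change only through that score.
- B: the correlation is pure measurement error in the baseline score. The biomarker follows true severity and is unrelated to change.

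**Interaction standard error.** Adding the covariate rescales the residual SD and costs one degree of freedom (94 − 5 = 89 to 94 − 6 = 88), a factor √(89/88) = 1.006. The adjusted/unadjusted ratio is

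- A: √[(1 − r²) / (1 − r²q²)] × 1.006
- B: √[1 − r² / (1 − q²)] × 1.006

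For example, A at r = 0.3, q = 0.5: √(0.91 / 0.9775) × 1.006 = 0.970. B at r = q = 0.5: √(1 − 0.25/0.75) × 1.006 = 0.821.

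| r | q | Ratio, A | Ratio, B |
|---|---|---|---|
| 0 | any | 1.006 | 1.006 |
| 0.2 | 0.3 | 0.987 | 0.983 |
| 0.2 | 0.5 | 0.990 | 0.978 |
| 0.3 | 0.3 | 0.963 | 0.955 |
| 0.3 | 0.5 | 0.970 | 0.943 |
| 0.5 | 0.3 | 0.881 | 0.856 |
| 0.5 | 0.5 | 0.899 | 0.821 |

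So the standard error falls by 3 to 18% at r of 0.3 to 0.5. In sample-size terms, 1/0.97² = 1.06 and 1/0.82² = 1.49: the same precision without the covariate would need about 6 to 49% more patients. Simulation (4,000 trials per cell, ordinary least squares with and without baseline mRSS) matches these ratios to within about 0.002. For the median-split model it gives a fall of 3 to 16%. The two-sided 5% interaction test rejects in about 4 to 6% of trials in every cell, adjusted or not.

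**Prognostic main effect.** Share of simulated trials with two-sided p < 0.05, centred treatment coding, no biomarker effect of its own:

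| Mechanism | r / q | Without baseline mRSS | With baseline mRSS |
|---|---|---|---|
| A | 0.3 / 0.3 | 14% | about 5% |
| A | 0.5 / 0.5 | 67% | about 5% |
| B | 0.3 / 0.3 | about 5% | 15% |
| B | 0.5 / 0.5 | about 5% | 90% |

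Hand check at 0.5 / 0.5. Under A the unadjusted correlation is 0.25, so the expected t is 0.25/√(1 − 0.0625) × √89 = 2.44 and Φ(2.44 − 1.99) = 67%. Under B the adjusted partial correlation is 0.25/0.75 = 0.333, so the expected t is 0.333/√(1 − 0.111) × √88 = 3.32 and Φ(3.32 − 1.99) = 91%.

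Treatment coding also matters, and the SAP does not state it. With 0/1 coding the main effect is the placebo-arm slope, and the unadjusted rate under A at 0.5 / 0.5 is 39%.

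**The case against.** The strongest case on the other side has four parts.

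- **The analysis is exploratory.** SAP 2.4.4.3 makes exploratory efficacy p-values descriptive, and 2.4.8 speaks only of a potential effect. This stands and limits the weight of the point. It does not make a wider interval preferable when the covariate is already in hand.
- **A marker that forecasts change because it follows severity is prognostic in the marginal sense.** This stands. Whether the effect should be read marginally or given baseline mRSS is a choice of estimand. The SAP does not say which it means.
- **The correlations are assumed.** This stands. The gain in precision is small when r is small and absent when r is zero.
- **Adjustment is not always harmless.** This stands for the main effect. Protocol 9.5 itself points to inter-rater variability in mRSS, and under mechanism B adjusting for the error-prone score creates the spurious association.

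A reader might infer that a biomarker which merely follows skin severity will be declared prognostic, and that adding baseline mRSS cures this at no cost. The documents do not support either statement. The result under A reverses under B, nothing in the documents says where between them the truth lies, and there is no declaration rule. A reader might also infer that the omission produces false predictive findings. It does not under the assumptions here, because the interaction test keeps its size.

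**Conclusion.** The omission is real and no reason is given for it. What holds under both mechanisms is the loss of precision for the predictive interaction: at assumed baseline-change correlations of 0.3 to 0.5, adjustment would lower its standard error by roughly 3 to 18%. At 0.2 the gain is about 1 to 2%, and with no correlation there is a loss of about 0.6%. Validity of that test is not at issue as long as baseline mRSS does not modify the treatment effect.

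For the prognostic term the conclusion is narrower: as specified, it cannot show value beyond baseline skin severity. The direction and size of any misreading depend on correlations and a mechanism that the documents do not supply. The point concerns one exploratory analysis; the primary analysis and its 80% power are untouched.

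**What to change.** In SAP 2.4.8, add baseline mRSS as a continuous covariate to both the continuous and the median-split biomarker models. Report the prognostic main effect with and without baseline mRSS, each labelled, and state the treatment coding so that the reader knows whether the main effect is an average slope or the placebo slope.

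The cost is one extra model run per biomarker, one degree of freedom, and care in reading the adjusted prognostic term given measurement error in the baseline score. The covariate is already collected and used in the primary model.
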